Statistical Analysis Plan

Study Title: The effects of PF-04995274 on emotional processing in treatment-resistant, medicated, depressed patients (RESTART study).

CT REGISTRATION: NCT03515733. ETHICS REF: 18/SC/0074

Objectives

The primary aim of the study is to investigate the effects of 7 days of PF-04995274 administration (adjunctive to SSRI/SNRI medication) on behavioural measures of non-emotional and emotional cognition, specifically memory performance on an auditory verbal learning task and performance (including accuracy and reaction times) on a facial expression recognition task. The secondary aim of the study is to investigate the effects of 7 days of PF-04995274 administration (adjunctive to SSRI/SNRI medication) on other behavioural measures of non-emotional and emotional cognition.

Brief summary of design

This study uses a double-blind, placebo-controlled, randomised between-groups design. Participants are patients who fulfil criteria for current episode of Major Depressive Disorder (MDD) and are currently taking an SSRI/SNRI and have failed to response clinically. Participants will be randomised to receive 7-9 days treatment with either PF-04995274 (15 mg daily) or a matched placebo. This study includes three visits in total: (a) Screening Visit; (b) First Dose Visit; (c) Research Visit Two. All visits will take place at the Warneford Hospital, Oxford University Department of Psychiatry.

Determination of Sample Size

We will recruit 50 participants to the study (25 on PF-0499574 and 25 on placebo). Participants who withdraw during the study or do not provide complete data-sets will be replaced. Based on data acquired in Harmer et al., (2004) comparing citalopram to placebo, if we aim for 0.9 power and a 0.05 false positive rate, a suggested group sample size is 19 (G*power) to ensure determination of group level differences at this variable if they exist. As 5HT4 agonism is less well studied, and to account for the exclusion of low quality data before analysis, we will aim for 25 individuals with complete datasets per group (total sample size of 50).

Data Cleaning

- Will be performed prior to unblinding
- Outliers will be excluded on a per task basis
- For all behavioural data, excluding the EPS, cut-off thresholds will be determined based on a visual inspection of a histogram plot, examining thresholds for:
 - > Trials with unusually low response times
 - > Trials with unusually high response times

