 - Proportion of missing/removed trials per participant
 - Abnormally low mean accuracy (or equivalent outcome) per participant
 - Abnormally high mean reaction time per participant
- For all self-report data, extreme outliers indicating invalid data entry will be determined based on a visual inspection of a histogram plot
- For emotion potentiated startle data, two researchers will independently a) distinguish startle blink response from noise and decide whether a response could have been seen, had one occurred, excluding trials if no response could not be seen and b) determine if there is a blink response or if the trial should be recorded as a non-response. If there is disagreement, a third researcher will make a final decision.

Behavioural Analysis

Below is a non-exhaustive list of outcomes and analyses which will be conducted.

Behavioural Task	Outcomes	Analysis		
		 All key endpoints will be summarized (mean, standard deviation) in tables and bar charts (mean ±SEM) 		
		Conducted in R (version will be confirmed in publications)		
Facial Expression	Unbiased hit rate, as described by Wagner (1993) – a	Repeated measures analyses of variance (ANOVAs):		
Recognition Task (FERT)	measure of emotion identification accuracy which	Between-subject factor – 2 levels: Treatment group (PF-		
	accounts for response bias i.e. any general tendency to	04995274 or placebo)		
Recognition of computer-	identify the emotion when it is not present. Calculated as	Within-subject factor – 7 levels (Fear, anger, happy, surprise,		
based positive and negative	proportion of correct hits * (number of hits/all hits and	disgust, sad, neutral)		
facial expressions	misses), for each facial expression category.			
	% correct and response bias will also be reported			
P1vital® Limited Products	individually.			
	Misclassifications: Number of responses to each facial			
	expression category incorrectly classified as another facial			
	expression category e.g. identifying a fearful face as			
	surprised			
	Reaction time (ms) for trials with correct responses.			
Auditory Verbal Learning	Number of words recalled -	Repeated measures analyses of variance (ANOVAs):		
Task (AVLT)	List A immediate recall trials	 Between-subject factor – 2 levels: Treatment group (PF- 04995274 or placebo) 		
Recall of words read aloud		Within-subject factor - 5 levels (List A immediate recall trials 1-5)		

Pen and paper	Number of words recalled -	Repeated measures analyses of variance (ANOVAs):

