Visual Analogue Scales (VAS)	Total score for each VAS (happy, sad, hostile, alert, anxious, calm)	Pre-ETB, Post-ETB)	
Side effects	Presence of side effect Severity of side effect Belief in relationship to drug	Descriptive report of frequency of side-effects for each group at four time points (baseline, pre-dose, post-dose and all other study days combined).	
		A generalised linear model will be used to analyse side effects, with presence of side-effect as outcome and predictors including treatment group (PF-04995274 or placebo) and time point (baseline, pre-dose, post-dose, day 2/3/4/5/6/7/8/9).	
		For side effects significantly associated with group and time-point, we will investigate severity and belief in relationship to study drug.	

When conducting ANOVAs, the Greenhouse-Geisser procedure will be used to correct the degrees of freedom where assumptions of equality of variance are violated. If there is a significant group x condition interaction found in ANOVAs. Post hoc independent samples t tests will be performed to follow up any significant interactions. We will not use the Bonferroni correction for multiple comparisons for post-hoc tests. When conducting t tests, degrees of freedom will be corrected where the assumption of equal variances between groups is violated (i.e. Levene's Test is significant).

Record of version changes and unblinding

Date	Version	Blinding Status	Comments
28 th October 2022	1.0	Team blinded, barring unblinding for study medics (AdeC, PC and BG) where necessary.	Data collection complete. First version of complete stats plans. Uploaded to clinicaltrials.gov and OSF.

Study Team involved in analysis

AdeC - [name] [name] - DPhil Student, Study Medic

AG - [name] – Post-doctoral Researcher

BG - [name] - Study Medic

CH - [name] - Principal Investigator

MB - [name] - Research Assistant

PC - [name] – Principal Investigator, Study Medic

SM - [name] - Senior Research Fellow

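### The side-effect GLM has no provision for symptoms reported in one arm only: the odds ratio is then infinite, and under default Wald tests the symptom would miss the severity and relatedness follow-up

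*SAP*

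**What the plan says.** The point concerns the side-effects row of the self-report table in the SAP's Behavioural Analysis section. That row sets out three steps.

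- A tabulation that does not depend on any test: "Descriptive report of frequency of side-effects for each group at four time points".
- A model: "A generalised linear model will be used to analyse side effects, with presence of side-effect as outcome and predictors including treatment group" and "time point (baseline, pre-dose, post-dose, day 2/3/4/5/6/7/8/9").
- A follow-up that depends on the model: "For side effects significantly associated with group and time-point, we will investigate severity and belief in relationship to study drug".

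The row does not give the link, the estimator, the test (Wald, likelihood ratio or other), the reference time point, or what happens when an arm or a time point has no reports. The section on sample size says "We will recruit 50 participants to the study (25 on PF-0499574 and 25 on placebo"). The header of the behavioural task table says "Conducted in R (version will be confirmed in publications"), which I take to cover this row too. The SAP gives no expected side-effect rates.

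**The concern.** With a yes/no outcome and 25 people per arm, a symptom can easily be reported on drug and never on placebo. The data are then quasi-completely separated by group. The likelihood keeps rising as the log odds ratio goes to infinity, so the fit stops wherever the software's convergence rule stops it, with a very large standard error. A Wald test divides one by the other and gives p near 1. If nobody reports the symptom at baseline and baseline is the reference level, each time contrast behaves in the same way.

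At stake is the last step of the row. Symptoms found only on drug are those for which severity and believed relatedness are most worth examining. Under one permissible way of reading the model they would be the ones left out. Under any reading, the ordinary fit gives no odds ratio or interval to report for them.

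**Working it through.** **Inputs.** From the SAP: 25 per arm; group and time point as predictors; a significance condition on both. My assumptions: binomial family with logit link, two-sided 0.05, and all event rates, since the SAP gives none. There is no SAP figure to reproduce for this row.

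**1. One record per person, 7/25 on drug against 0/25 on placebo.**

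- *Maximum likelihood.* Odds ratio = (7 × 25)/(18 × 0), which is infinite.
- *Wald.* Under R's default convergence rule the fit stops at log odds ratio 18.6 with SE 2,151, so z is 18.6 divided by 2,151, which is 0.009, and p = 0.993. A tighter rule gives 22.6 with SE 15,892 and p = 0.999. The exact values are artefacts of stopping; p near 1 is not.
- *Likelihood ratio.* Log-likelihood with separate rates: 7 ln(7/25) + 18 ln(18/25) + 0 = −14.82. With a common rate: 7 ln(7/50) + 43 ln(43/50) = −20.25. Twice the difference is 10.85 on 1 df, p = 0.001.
- *Fisher, two-sided.* 2 × C(25,7)/C(50,7) = 2 × 0.00481 = 0.0096.
- *Firth.* For a 2×2 table this equals adding one half to each cell: the odds are 7.5/18.5 = 0.405 on drug and 0.5/25.5 = 0.0196 on placebo, and their ratio is 20.7, with penalised likelihood-ratio p = 0.004. The estimate is finite.

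**2. Other counts against 0/25 (R default fit).**

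| Drug events | Wald p | Likelihood-ratio p | Fisher p |
|---|---|---|---|
| 3 | 0.996 | 0.037 | 0.235 |
| 5 | 0.996 | 0.006 | 0.0502 |
| 6 | 0.993 | 0.0025 | 0.022 |
| 8 | 0.993 | 0.0004 | 0.004 |
| 10 | 0.993 | 0.00005 | 0.0006 |

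The Wald p-value stays near 1 as the evidence grows. At 3 against 0, whether the symptom passes depends wholly on which test is chosen.

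**3. Repeated records, group plus time point, time taken as 11 levels.**

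- *Drug-only symptom, 1 to 8 of 25 at each time point.* Group coefficient 18.99, SE 1,036, Wald p 0.985; likelihood-ratio p < 2e-16. In 300 simulated trials with about 28% of drug participants affected, Wald flagged group in none, and Fisher on ever/never flagged it in 75%.
- *Symptom in both arms, none at baseline, baseline as reference.* All ten time coefficients lie between about 16 and 18, with SE 874 and Wald p 0.984 to 0.986. The omnibus likelihood-ratio test for time gives 31.9 on 10 df, p = 0.0004. Group is intact: 1.69, SE 0.28, p < 0.0001.
- *Same data, post-dose as reference.* Only the baseline contrast diverges; pre-dose against post-dose has Wald p 0.009.

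The likelihood-ratio p-values in this step treat repeated reports as independent, so they show the contrast with Wald and do not validate the model. In 400-run simulations with no group effect and an assumed participant random-intercept SD of 1.5 on the logit scale, type I error for group was about 0.22 to 0.30 with either test.

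**4. How often would a cell be empty?** With rate r, P(no placebo report among 25) = (1 − r)^25, where r is per participant over the study; P(no baseline report among 50) = (1 − r)^50, where r is the rate at baseline.

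| Assumed r | No placebo report | No baseline report |
|---|---|---|
| 1% | 0.78 | 0.61 |
| 2% | 0.60 | 0.36 |
| 5% | 0.28 | 0.08 |
| 10% | 0.07 | 0.005 |
| 20% | 0.004 | < 0.001 |

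**The case against.** A reader might infer that the planned GLM will itself overlook the most drug-specific symptoms. The SAP does not support that. It does not call for Wald tests, and a likelihood-ratio test on the same fit is strongly significant: in 100 simulated trials of the drug-only scenario it flagged group in all 100. A reader might also infer that an empty baseline defeats the whole model. That needs baseline as the reference level and a contrast-by-contrast reading, neither of which is stated; an omnibus test for time and the group effect both survive.

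Further points on the other side are fair. Eleven time levels is one reading; the tabulation in the same row pools the later days into a fourth category, and the model could do likewise. Sparseness is assumed, and depressed patients already taking an SSRI or SNRI may report many symptoms in both arms, which makes empty cells rarer. A 7 against 0 split would be visible in the frequency table whatever the model shows, so the documents do not support a claim that a signal would be hidden. Side effects are not among the stated primary or secondary aims.

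Two things remain. A likelihood-ratio test rescues the p-value but not the estimate: the maximum-likelihood odds ratio is infinite under any test. And because the follow-up requires both group and time point, leaving the test open lets the same data pass or fail according to a choice that could be made after they are seen.

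**Conclusion.** The point holds in conditional form.

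- *Whatever the test:* a symptom reported in one arm only yields no usable odds ratio or Wald interval from an ordinary logistic fit.
- *If Wald p-values are read:* such a symptom has p near 1 (about 0.99 for 7/25 against 0/25, where Fisher gives 0.0096) and misses the severity and relatedness follow-up.
- *If, in addition, baseline is the reference level and has no reports:* the individual time contrasts fail in the same way, while an omnibus likelihood-ratio test and the group effect do not.

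The exposure is mainly to symptoms with a placebo rate of about 5% or less and is small from 10% upwards. These rates, the logit link and the 0.05 level are assumptions. The loss is confined to the estimate and the follow-up step. This should be corrected, but it does not touch the primary or secondary aims.

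**What to change.** For each side effect, reduce the data to one record per participant (any report after the first dose) and test group by one of the following, chosen before unblinding:

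- Firth-penalised logistic regression with a penalised likelihood-ratio test and profile-likelihood interval; or
- Fisher's exact test with an exact interval for the risk difference.

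Let that test decide which side effects go on to the review of severity and believed relatedness. Keep the time-point GLM as descriptive support. If time is still to be tested, use one omnibus test that is not a Wald test and that allows for repeated reports from the same person; Firth penalisation alone does not do that.

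The cost is a sentence or two in the SAP and a different R function. Firth shrinks odds ratios slightly. Fisher is somewhat conservative: 5/25 against 0/25 gives 2 × C(25,5)/C(50,5) = 2 × 53,130/2,118,760 = 0.0502 and just misses 0.05. Either option takes the time condition out of the trigger, although counting only reports after the first dose keeps the part of timing that matters most here. Using one record per participant also removes the clustering problem from the trigger.

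### Severity and believed drug-relatedness are examined only for side effects whose presence is statistically significant, a condition that cannot respond to a difference in severity alone

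*SAP*

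**What the plan says.** The Side effects row of the Behavioural Analysis table names three outcomes: "Presence of side effect Severity of side effect Belief in relationship to drug". It then sets out three steps.

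- A summary with no condition attached: "Descriptive report of frequency of side-effects for each group at four time points". This covers frequency only.
- A generalised linear model "with presence of side-effect as outcome and predictors including treatment group (PF-04995274 or placebo) and time point". The outcome is presence. The SAP names neither the test nor the significance level, and does not say whether a side effect must show two main effects or an interaction.
- A conditional step: "For side effects significantly associated with group and time-point, we will investigate severity and belief in relationship to study drug".

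No other sentence in the SAP provides for a summary of severity or believed relatedness. Under Determination of Sample Size, the trial has 25 participants per arm: "We will recruit 50 participants to the study (25 on PF-0499574 and 25 on placebo".

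**The concern.** Two of the three listed side-effect outcomes are opened only if a test on the third is significant. This causes two distinct problems.

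First, the test looks at the wrong quantity. All participants are depressed and taking an SSRI or SNRI, and side effects are recorded at baseline, so some symptoms may well be present in both arms. If the study drug makes such a symptom worse without making it more frequent, the presence test has nothing to detect.

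Second, 25 per arm gives limited power for uncommon symptoms, and non-significance at that size is not evidence that a symptom is harmless.

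In either case the report could give counts of a symptom by arm without saying whether the cases were mild or severe, or whether they were thought to be drug-related, although both were listed as outcomes.

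**Working it through.** **The plan's own figure.** The SAP gives no side-effect rate or power. Its only sample-size figure concerns cognition: "if we aim for 0.9 power and a 0.05 false positive rate, a suggested group sample size is 19 (G*power". No effect size is stated, so 19 cannot be reproduced directly. Back-solving with the noncentral t gives a standardised difference of about 1.08 to 1.11 two-sided, or 0.97 to 1.00 one-sided. None of this bears on side effects.

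**Inputs.** From the SAP: 25 per arm, binary presence as the tested outcome. Assumed, because the SAP does not state them: two-sided 0.05, one presence/absence comparison per participant, and the side-effect rates. As the test is not named, three are shown: Fisher exact, uncorrected chi-square, and the likelihood-ratio test from a logistic model with group as the only predictor.

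**Step 1: severity-only difference.** With equal presence in both arms, the chance of meeting the condition is the false-positive rate of the presence test. Summing Bin(a; 25, 0.4) × Bin(b; 25, 0.4) over all pairs (a, b) with p < 0.05 gives 0.03 (Fisher) and 0.06 (chi-square and likelihood ratio). At 50% or 60% presence the Fisher and chi-square results are again 0.03 and 0.06. Severity does not enter the calculation, so no severity difference changes the result. For contrast, take an invented split among 10 affected per arm, 8 severe on drug and 2 on placebo: a direct Fisher comparison gives p = 0.023.

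**Step 2: how many cases are needed against none on placebo.** Formulas for k v 0:

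- Fisher: p = 2·C(25,k)/C(50,k). For k = 3, 2 × 2300/19600 = 0.235.
- Chi-square: z² = (k/25)² / [p̄(1 − p̄)·2/25], p̄ = k/50. For k = 4, 0.0256/(0.08 × 0.92 × 0.08) = 4.35, p = 0.037.
- Likelihood ratio: G = 2[ℓ(k,25) − ℓ(k,50)], where ℓ(k,m) = k·ln(k/m) + (m − k)·ln(1 − k/m). For k = 3, 2 × (−9.173 + 11.348) = 4.35, p = 0.037.

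| Drug v placebo cases | Fisher | Chi-square | Likelihood ratio |
|---|---|---|---|
| 3 v 0 | 0.235 | 0.074 | 0.037 |
| 4 v 0 | 0.110 | 0.037 | 0.015 |
| 5 v 0 | 0.0502 | 0.018 | 0.006 |
| 6 v 0 | 0.022 | 0.009 | < 0.006 |

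The smallest passing count is therefore 6, 4 or 3, depending on the test.

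**Step 3: chance of meeting the condition.** With a placebo rate of 0 this is P(X ≥ k*), X ~ Bin(25, rate), k* = 6, 4 or 3. With a non-zero placebo rate, the double sum of Step 1 is used with unequal rates.

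| Assumed true rates | Fisher | Chi-square | Likelihood ratio |
|---|---|---|---|
| 12% v 0% | 7% | 35% | 59% |
| 20% v 4% | 23% | 44% | 49% |
| 20% v 0% | 38% | 77% | 90% |

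**What the single comparison leaves out.** The planned model uses repeated time points and states no within-participant term. Treating records as independent could let a persistent symptom pass with fewer participants. Also requiring an association with time point could make passing harder. With no placebo events a logistic model has separation, so a Wald test would fail. None of these makes the condition respond to severity.

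**The case against.** The strongest reply is that little is actually hidden. Frequency is reported by group for side effects whatever the test shows, so a reader who infers that an uncommon severe symptom goes unexamined altogether would be wrong. Only its severity and believed relatedness are conditional.

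A reader might also infer that any symptom seen in up to 20% of drug participants and in no placebo participant escapes severity review, or that 3 v 0 must be non-significant. The SAP does not support either statement. Both hold under Fisher's test, but the SAP plans a generalised linear model with an unnamed test; under a likelihood-ratio test 3 v 0 passes, and 20% v 0% passes 90% of the time.

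Nor is a tolerability conclusion at stake in the SAP's own terms: its Objectives are cognitive. Severity grading, causality assessment and listing of individual severe events are commonly left to a protocol, which is not at hand, and their absence here is no fault.

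Finally, the table is introduced as non-exhaustive, and the conditional sentence can be read as extra follow-up. That permits a fuller summary but commits to none; the only stated rule for severity and relatedness is conditional. The argument that a presence test cannot see severity needs no assumed rate, and it stands.

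**Conclusion.** The point holds as a fault in a stated rule, and it concerns descriptive reporting. The structural part is firm: the condition tests presence, so a severity-only difference meets it only by chance, about 3% to 6% at an assumed 40% presence in both arms. The part about uncommon symptoms is a range, not a single figure. Between 3 and 6 cases against none are needed, and the chance of passing is often limited but reaches 90% in the most favourable case shown. These figures assume one 25 v 25 comparison, two-sided 0.05, and rates that the SAP does not give. The change is worth making because it is cheap and the outcomes are already listed. The primary cognitive conclusions do not depend on it.

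**What to change.** Remove the significance condition for description. For every side effect, tabulate by arm the number of participants at each severity level, showing worst post-dose severity alongside baseline, and the number of participants in whom it was believed drug-related. Keep the generalised linear model as a supplement, and state that its result does not decide which side effects have severity and relatedness reported.

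The cost is a short change of SAP wording, recorded as a new dated version, and a longer side-effect table. The version record says that data collection is complete, and the change needs no new data. It spends no alpha because the added output is descriptive.

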Recognition of emotional words from ECAT	Reaction time	
P1vital [®] Limited Products		

Facial Dot Probe Task	Vigilance scores derived from reaction time – e.g. bias	Mixed models analyses of variance (ANOVAs).
(FDOT) Vigilance to fearful and happy faces P1vital® Limited Products	scores calculated by subtracting median reaction times in congruent trials (i.e. the probe appears behind the emotional expression) from those in incongruent trials (i.e. the probe appears behind the neutral expression)	 Between-subject factor – 2 levels: Treatment group (PF-04995274 or placebo) Within-subject factors 2 levels: Emotion (positive or negative) 2 levels: Probe duration (masked or unmasked)
Emotion Potentiated	Raw amplitude of startle response	Mixed models analyses of variance (ANOVAs).
Startle (EPS)	Raw amplitude of startle response	Between-subject factor – 2 levels: Treatment group (PF- 04995274 or placebo)
EMG data, in response to white noise during positive or negative images	Z-transformed amplitude of startle response	 Within-subject factors – 2 levels: Trial type (positive, negative, neutral)
San Diego Instruments, San Diego, CA, USA	Latency of startle response (ms)	
Oxford Memory Test (OMT)	Proportion of correct probe selections	Mixed models analyses of variance (ANOVAs). Between-subject factor – 2 levels: Treatment group (PF-
Visual short term spatial memory	Absolute error for probe location Reaction Time	 04995274 or placebo) Within-subject factors – 2 levels: Trial condition (1 or 3 memory probes)
Oxford Memory Test application "Short_Fractals1" — modified from "What was where task" (Pertzov et al., 2013) running on iOS 12.3.1		

Self-report or researcher-observed scale – all completed on Qualtrics.XM (https://www.qualtrics.com) except HAM-D			
Eysenck Personality Questionnaire (EPQ)	Total score for each dimension	Report descriptives for each group	
State and Trait Anxiety Inventory –	Total score		
Trait subscale (STAI-T)			
Becks Depression Inventory (BDI)	Total score		
Hamilton Depression Scale (HAM-D)	Total score		
Pen and paper – scored by research team			
Snaith-Hamilton Pleasure Scale (SHAPS)	Total score		
State and Trait Anxiety Inventory –	Total score	Mixed model ANOVAs:	
State subscale (STAI-S)		Between-subject factor – 2 levels: Treatment group (PF-04995274 or	
Positive and Negative Affect Scale	Total score for positive and negative	placebo)	
(PANAS)	subscales	• Within-subject factors – 4 levels: Time condition (Pre-scan, Post-scan,	

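### The Greenhouse-Geisser correction is tied to equality of variance instead of sphericity, so interaction tests with three or more levels can go uncorrected

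*SAP*

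**What the plan says.** The rule for ANOVAs stands in the paragraph between the analysis tables and the version record: "the Greenhouse-Geisser procedure will be used to correct the degrees of freedom where assumptions of equality of variance are violated". Neither sphericity nor a test of it appears anywhere in the SAP. The t-tests have their own rule in the same paragraph: "degrees of freedom will be corrected where the assumption of equal variances between groups is violated". Only there does the SAP say which variances are compared and name Levene's test.

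The paragraph also states what follows from a significant interaction: "Post hoc independent samples t tests will be performed to follow up any significant interactions", and then "We will not use the Bonferroni correction for multiple comparisons for post-hoc tests".

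Within-subject factors with more than two levels, from the Behavioural Analysis and self-report tables:

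- AVLT immediate recall: "5 levels (List A immediate recall trials 1-5"
- FERT: "7 levels (Fear, anger, happy, surprise" and three further categories
- STAI-S, PANAS and VAS: "4 levels: Time condition (Pre-scan, Post-scan" and two further time points
- EPS: the row gives the number of levels as two but lists three trial types

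The Objectives section makes two of these tasks primary: "memory performance on an auditory verbal learning task and performance (including accuracy and reaction times) on a facial expression recognition task".

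**The concern.** Equal variances and sphericity are different conditions. The uncorrected within-subject F test is valid when the variances of all pairwise differences between levels are equal. That depends on the correlations as well as the variances. Repeated learning trials are an obvious case where it may fail, because neighbouring trials may well correlate more than distant ones even if every trial has the same SD.

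The sentence does not say whether variances are compared across the within-subject levels or between the groups. Across levels is the more natural literal reading, since the between-group comparison and Levene's test belong to the t-test sentence. Under either reading, the check can pass while sphericity fails, and an analyst following the text would then leave the degrees of freedom uncorrected.

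At stake is the type I error of the group-by-condition test on both primary tasks. Because that test opens the unadjusted post hoc comparisons, a liberal test lets them be run more often than intended. Group main effects, two-level factors and stand-alone t-tests are not affected.

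**Working it through.** **Inputs from the SAP.** 25 per group (N = 50), alpha 0.05, k levels as listed above. The SAP states no covariances and no type I error figure for these tests, so there is no figure of its own to reproduce. All correlations and SD patterns below are assumptions.

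**Step 1: equal variances do not give sphericity.** For levels with unit variance, Var(Yi − Yj) = 2(1 − ρij). Take five trials with first-order autoregressive (AR(1)) correlation 0.8:

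- adjacent trials: 2(1 − 0.8) = 0.40
- trials 1 and 5: 2(1 − 0.8⁴) = 2(1 − 0.4096) = 1.18

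The variances are identical, yet the variances of differences differ by a factor of 1.18/0.40 ≈ 2.95.

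**Step 2: degree of departure.** With S the covariance matrix of k − 1 orthonormal contrasts, ε = (tr S)² / [(k − 1) tr(S²)]. It equals 1 under sphericity and is at least 1/(k − 1). For five equal-SD trials ε is 1.000 under compound symmetry, and 0.919, 0.749, 0.631 and 0.551 under AR(1) correlation 0.3, 0.6, 0.8 and 0.95. With k = 2, ε is always 1.

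**Step 3: worst-case bound with no correction.** The interaction F has k − 1 and (k − 1)(N − 2) degrees of freedom: 6 and 288 for the FERT, 4 and 192 for the AVLT, 3 and 144 for the mood scales, 2 and 96 for the EPS if three levels are analysed. At minimum ε, the size is P(F(1,48) > uncorrected critical value): 15.1%, 12.6%, 10.9% and 8.5% respectively. These are limits, not expectations.

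**Step 4: the AVLT under the rule as written.** Null simulations (multivariate normal, 25 per arm, 100,000 runs per cell, 95% Monte Carlo error about ±0.14 to 0.18 points). The SAP names no variance test for the ANOVAs, so Levene's test at 0.05 stands in for one. SD changes linearly over the trials; the SD ratio is the largest SD over the smallest. Type I error of group × trial, %:

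| Trigger | SD ratio | Compound symmetry 0.5 | AR(1) 0.3 | 0.6 | 0.8 | 0.95 |
|---|---|---|---|---|---|---|
| Variances across trials | 1 | 4.9 | 5.4 | 6.6 | 7.4 | 8.2 |
| Variances across trials | 1.3 | 4.9 | 5.3 | 6.2 | 7.0 | 8.4 |
| Variances across trials | 1.5 | 4.8 | 5.0 | 5.6 | 6.4 | 7.3 |
| Variances across trials | 1.8 | 4.6 | 4.7 | 5.0 | 5.2 | 5.3 |
| Variances between groups | 1 | 4.8 | 5.2 | 6.2 | 6.9 | 7.8 |
| Variances between groups | 1.8 | 5.4 | 5.6 | 6.5 | 7.4 | 8.9 |

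Over the 20 combinations of correlation and SD ratio, Mauchly-triggered correction gives 4.7 to 5.1% and unconditional correction 4.4 to 5.1%. The reason shows in how often the triggers fire. At AR(1) 0.6 to 0.8, the across-trial variance check fires in 1 to 3% of runs with equal SDs and in 89 to 90% at SD ratio 1.8. Mauchly's test fires in 98 to 100%.

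**Step 5: the other factors** (40,000 runs per cell, error about ±0.2 to 0.3 points).

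- FERT, compound symmetry 0.3: 4.3 to 5.0% (across-level trigger), 4.8 to 5.2% (between-group).
- FERT, fear, anger, disgust and sad clustered against the rest, correlation 0.4 within and 0.2 between: across-level 5.7% with equal SDs and 4.5% with SDs from 0.8 to 1.4; between-group 5.4 to 5.7%.
- FERT, clustering 0.6 and 0.2: across-level 7.7% and 5.0%; between-group 6.8% and 7.3%. Mauchly-triggered correction gives 4.5 to 5.0% in all FERT cells.
- Mood scales, across-level: 4.9% (compound symmetry, equal SDs), 6.0 to 6.7% (AR(1) 0.6 to 0.8, equal SDs), 4.8 to 5.4% (SD ratio 1.8).
- EPS with three levels, AR(1) 0.6 to 0.8, equal SDs: 5.6 to 5.7% under either trigger.

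**Step 6: what reaches the post hoc tests.** On the AVLT, the chance that the gate opens and at least one t-test has p < 0.05 is 1.4 to 4.8% under either variance trigger, against 1.0 to 4.3% with Mauchly. The same-cell difference runs from −0.1 to +1.1 points.

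**The case against.** The best defence is that sphericity was meant. Greenhouse-Geisser serves to correct for non-sphericity, sphericity is itself an equality of variances (of differences), and the SAP gives t-tests a separate rule with its own test. The unqualified phrase could therefore be shorthand. That is plausible, and if the team tests sphericity, nothing but the wording is wrong. Nothing in the text confirms it, though, and the same paragraph uses equal variances in the ordinary sense for the t-tests.

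A second objection is that the figures describe triggers the SAP does not specify, and that Levene's test is not designed for correlated measurements. This stands as a limit on the numbers: they illustrate, and do not estimate, the error in this trial. It does not rescue the rule, since any check of the variances alone misses the part of sphericity that depends on correlations.

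A third is that the harm is small. This also stands in part. Inflation is absent under compound symmetry with equal SDs, and it nearly disappears at SD ratio 1.8 under the across-level reading. The largest AVLT values need a correlation of 0.95. FERT inflation in these runs depends on an assumed clustering of emotions. AVLT post hoc claims stay below 5% throughout; no such figure was computed for the FERT. The decision not to use Bonferroni is a separate, explicit choice, and the EPS level count is a separate slip. Neither adds weight to this point.

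**Conclusion.** The concern holds: the rule as written names the wrong assumption. It can leave the interaction tests for the AVLT trials, the FERT and the mood scales uncorrected when sphericity fails, and the EPS test too if three levels are analysed. With equal SDs and AR(1) correlation of 0.3 to 0.8, the AVLT test would run at 5.4 to 7.4% on the across-level reading, or 5.2 to 6.9% on the between-group reading, instead of 5%. Other assumptions span no inflation to nearly 9%. The effect on false AVLT post hoc claims is about one point at most. These sizes rest on assumed covariances, normal data and Levene's test as a stand-in trigger; that equal variances do not imply sphericity rests on none of these. The point should be corrected because it touches both primary tasks and the remedy is nearly free, but it is not shown to threaten the trial's conclusions.

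**What to change.** In the ANOVA sentence, replace the equality-of-variance condition with: where sphericity is violated (Mauchly's test), for within-subject effects and interactions with more than two levels. Applying Greenhouse-Geisser to all such effects without a pretest is equally acceptable. Keep Levene's test for the between-group t-tests. Reconcile the EPS row's level count with its three listed trial types, and apply the same rule if three are analysed. Enter the change in the SAP's version table with the blinding status at that date.

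The cost is one phrase and one table row, with no new data. The power cost when sphericity holds (correlation 0.3, effect in one level only) is, in %:

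| Task, effect | Uncorrected | Mauchly | Always |
|---|---|---|---|
| AVLT, d = 1.08 | 91.7 | 91.6 | 91.0 |
| FERT, d = 1.08 | 90.4 | 90.2 | 89.0 |
| AVLT, d = 0.7 | 53.0 | 52.8 | 51.0 |
| FERT, d = 0.7 | 48.7 | 48.5 | 45.7 |

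The loss is 0.1 to 0.2 points with Mauchly (at most about 0.3 allowing for rounding) and 0.7 to 3.0 points if always applied. The SAP states no effect size. The value 1.08 is what its 19 per group at 0.9 power implies for a two-sided 5% two-sample t-test, and 0.7 is assumed.
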